9.4.4 ANALYSIS OF SAFETY

The inclusion of randomized, blinded normal saline controls allows unbiased collection of AE data. Because normal saline is physiologically inert, the rate of AEs recorded in normal saline recipients will represent background rates in the population. The use of any vaccine comparator other than normal saline would make it impossible to measure AEs due to PfSPZ Vaccine because these would be obscured by AEs caused by the comparator vaccine.

AEs and laboratory abnormalities will be analyzed based on the safety cohort dataset. Solicited local and systemic adverse events will be assessed individually and as total local or systemic adverse events. Unsolicited adverse events will be classified by the Medical Dictionary for Regulatory Activities (MedDRA) at the preferred term level and also will be assessed individually and as total unsolicited adverse events. The overall percentage of participants with a solicited local adverse event, a solicited systemic adverse event, an unsolicited adverse event, a laboratory abnormality or an SAE during the appropriate surveillance periods after immunization will be tabulated. The severity and relationship to study product will be tabulated as well. Rates of adverse events will be compared between vaccine and control groups and compared statistically using Fisher's exact test. In addition, laboratory abnormalities deemed clinically relevant will be tabulated by study group and rates of occurrence compared between vaccinees and controls.

9.4.5 ANALYSIS OF ANTIBODY RESPONSES, CORRELATES OF PROTECTION

Antibody levels to PfCSP by ELISA as the initial measure of immunogenicity assay will be measured at specified time points. Immunofluorescence assay (IFA) and inhibition of sporozoite invasion (ISI) may also be measured as exploratory analyses. Pre- immunization and post-immunization responses will be compared for vaccinees vs. placebo recipients. Tables and figures will be prepared showing these comparisons using:

- for antibodies to PfCSP by ELISA, reciprocal titers at optical density 1.0 (OD1.0) with background (medium control) subtracted, and ratios of values post-immunization compared to pre-immunization.
- for antibodies to sporozoites by automated immunofluorescence assay, reciprocal titers providing arbitrary fluorescence units of 2×10^5 with background (medium control) subtracted.

- for inhibition of sporozoite invasion, percent reduction of the numbers of PfSPZ that invaded a human hepatocyte line in the presence of post-immunization serum as compared with pre-immunization serum.

Correlations with protection will be done using non-parametric tests based on rank, such as the Spearman rank correlation coefficient. Association between categorical measures will be assessed using chi-square or exact tests. Effects of any covariates (e.g. age) will be assessed using regression models.

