3.2 OBJECTIVES AND ENDPOINTS

OBJECTIVES	ENDPOINTS	JUSTIFICATION FOR ENDPOINTS
Primary		
To measure the combined vaccine efficacy (VE) of PfSPZ Vaccine against Pf malaria in adults living in the US following heterologous controlled human malaria infection (CHMI) with PfSPZ Challenge (7G8) administered 3 or 12 weeks after last dose of vaccine, in the modified intention-to-treat (mITT) population.	VE computed as one minus the estimated risk ratio for Pf infection (parasitemia) detected by qRT-PCR beginning 7 days after CHMI and censoring participants at 28 days in the “modified Intention to Treat” (mITT) population, combining data across the three CHMI timepoints.	Complete protection against infection during CHMI (i.e., no parasitemia) is a primary measure of PfSPZ Vaccine VE.
To assess safety and tolerability of 3 doses of 9.0×10^5 PfSPZ of PfSPZ Vaccine administered by direct venous inoculation (DVI) on days 1 (V1), 8 (V2) and 29 (V3).	The differences in proportions of vaccinees compared to controls experiencing related solicited and unsolicited adverse events and laboratory abnormalities after vaccination.	The number and nature of solicited and unsolicited adverse events, SAEs and abnormal laboratory values will provide an objective measure of safety and tolerability of the investigational product (IP).
Secondary		
To measure VE separately at each CHMI timepoint (3 and 12 weeks after V3).	VE measured as above, for each timepoint.	Determination of VE at each of the two CHMI timepoints will provide information useful for prescribing PfSPZ Vaccine.
To measure antibody responses to PfCSP 2 weeks after V2 and V3, on the day of CHMI and 4 weeks post-CHMI and determine if antibody responses are correlated with protection.	Antibody levels to PfCSP measured by ELISA comparing vaccinees to controls and protected (no parasitemia occurring post CHMI) and non-protected (parasitemia occurring post CHMI) vaccinees.	Antibody studies are important measures of the immunogenicity of the vaccine and have shown an association with protection in prior studies.
Tertiary/Exploratory		
To compare VE between groups with CHMI 3 or 12 weeks after V3.	VE measured as above.	Determination of VE across the span of a 12-week travel period will provide information useful for prescribing PfSPZ Vaccine

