8.2.3 IMMUNOLOGY LABORATORY EVALUATIONS

8.2.3.1 ANTIBODY

Time points: pre-immunization, 2 weeks after V2, 2 weeks after V3, CHMI, 28 days post CHMI.

Table 9. Antibody Assays

anti-CSP ELISA (all), IFA and ISI (exploratory); ELISA for other antigens (exploratory), systems serology	Serum 25 mL	3-week CHMI: pre-V1, D15, D43, D50, D78 12-week CHMI: pre-V1, D15, D43, D113, D141
---	----------------	---

Sanaria will conduct its standard ELISA to determine levels of antibodies to Pf circumsporozoite protein (CSP) and may also conduct whole PfSPZ immunofluorescence assay (IFA), inhibition of sporozoite invasion assay (ISI) and ELISA's using other Pf antigens. The laboratory of [name], Professor of Medicine at Harvard Medical School and a Group Leader at the Ragon Institute of MGH, MIT and Harvard, has developed a number of antibody profiling approaches that allow deep interrogation of the role of antibodies in the response to immunization and pathogens. The lab has a particular interest in malaria and malaria vaccines with a goal to understand the role of antibodies in protection against infection following immunization with PfSPZ Vaccine. As a contribution to the USSPZV7 trial, the lab will conduct relevant systems immunology assays including biophysical measurements (isotype, subclass, Fc-receptor binding levels), antibody effector function assays, as well as potential malaria restriction assays in primary human livers.

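### The antibody correlate analysis names rank tests with no CHMI-cohort term, and its objective includes a serum drawn after the outcome

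*Combined protocol and SAP*

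**What the plan says.** The secondary objective in section 3.2 reads "To measure antibody responses to PfCSP 2 weeks after V2 and V3, on the day of CHMI and 4 weeks post-CHMI" and goes on to ask whether the responses are correlated with protection. Its endpoint compares vaccinees with controls, and "protected (no parasitemia occurring post CHMI) and non-protected (parasitemia occurring post CHMI) vaccinees".

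On method, section 9.4.5 states "Correlations with protection will be done using non-parametric tests based on rank, such as the Spearman rank correlation coefficient". The immunogenicity paragraph of section 9.2 names Wilcoxon and Spearman for infected against non-infected participants, with the aim of finding a threshold response. On adjustment, section 9.4.5 says only "Effects of any covariates (e.g. age) will be assessed using regression models". Section 9.4.6 uses the same approach for cellular responses, with age and ethnicity as its examples.

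Table 9 in section 8.2.3.1 gives the serum days: "3-week CHMI: pre-V1, D15, D43, D50, D78" and "12-week CHMI: pre-V1, D15, D43, D113, D141". Section 4.2 describes randomization to CHMI at 3 or 12 weeks, and section 6.6.1 blocks treatment allocation within each CHMI cohort.

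No section says whether the cohorts are pooled, stratified or analysed separately for the correlate, or which sample is the candidate correlate.

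**The concern.** There are two separate problems.

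**Time since vaccination.** The same nominal sample, day of CHMI, is nine weeks older relative to V3 in one cohort than in the other. A Spearman or Wilcoxon test over all vaccinees has no cohort term. If the 12-week cohort has both lower titres and less protection, low titre and infection will go together simply because both mark that cohort. A threshold search over the same mixture has the same weakness.

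**Order of events.** The objective's wording, "on the day of CHMI and 4 weeks post-CHMI and determine if antibody responses are correlated with protection", ties a serum taken 28 days after challenge to the correlate question. Section 2.2.1.3 reports parasitemia between days 7 and 17 with none detected later, and section 8.1.6.2 has every case treated. On that pattern, non-protected vaccinees have been infected and treated before this serum is drawn. A titre difference may then be a consequence of infection.

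At stake is the reading of a secondary objective. The primary VE analysis is not touched.

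**Working it through.** **Inputs from the plan.** The plan gives no power or size figure for the correlate analysis. The number of vaccinees comes from section 9.2: 45 less six drop-outs is 39. The figures there reproduce: VE = 1 - (20/39)/(12/13) = 44.4%, and the pooled-variance two-sided power for 12/13 against 20/39 is 83.2% (stated: 83%). I split the 39 as 20 and 19, assuming drop-out is even across cohorts.

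**Sample timing (V2 = D8, V3 = D29).**

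| Sample | 3-week cohort | 12-week cohort |
|---|---|---|
| D15 | V2+7 | V2+7 |
| D43 | V3+14 | V3+14 |
| Day of CHMI | D50 = V3+21 | D113 = V3+84 |
| Post-CHMI serum | D78 = CHMI+28 | D141 = CHMI+28 |
| Post-CHMI PBMC (Table 10) | D57 = CHMI+7 | D120 = CHMI+7 |

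Of the pre-challenge, post-vaccination sera, only day of CHMI differs in time since vaccination. (D15 is labelled 2 weeks after V2 but falls 1 week after it; that needs reconciling.)

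**Day-of-CHMI sample: closed form.** Suppose titre and protection are independent within each cohort. Let pA and pB be protection at 3 and 12 weeks, p their weighted mean, and d the fall in mean log titre in SD units. With nearly equal cohorts:

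- cohort-protection correlation: r1 = 0.5(pA - pB)/√(p(1 - p))
- cohort-titre correlation: r2 = 0.5d/√(1 + 0.25d²)
- spurious pooled correlation: r = r1 × r2
- z = atanh(r) × √(39 - 3), and rejection rate = Φ(z - 1.96) + Φ(-z - 1.96)

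If protection is equal, r1 = 0, so r = 0 and the rate is 5% whatever d is. If titre is equal, as expected at D43, r2 = 0 with the same result.

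- 83% to 70% (13 points), d = 1.25: r1 = 0.065/0.423 = 0.154; r2 = 0.625/1.179 = 0.530; r = 0.081; z = 0.49; rate about 8%.
- 60% to 38% (22 points), d = 1.25: r1 = 0.11/0.50 = 0.220; r = 0.117; z = 0.70; rate about 11%.
- 70% to 30% (40 points), d = 1.5: r1 = 0.20/0.50 = 0.400; r2 = 0.75/1.25 = 0.600; r = 0.240; z = 1.47; rate about 31%.

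**Simulation.** 4,000 trials per setting, 20 + 19 vaccinees, assumed SD 0.4 log10, two-sided 0.05. Falls of 0.15, 0.3 and 0.5 log10 are 0.375, 0.75 and 1.25 SD.

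| Protection, 3 to 12 weeks | Unstratified, fall 0.15 | 0.3 | 0.5 | Stratified (van Elteren), range |
|---|---|---|---|---|
| 49% to 49% | 4.7% | 5.1% | 5.0% | 4.7-5.2% |
| 83% to 83% | 5.2% | 4.9% | 4.6% | 4.5-4.9% |
| 60% to 38% | 5.8% | 7.7% | 11.4% | 5.1-5.6% |
| 70% to 28% | 6.7% | 15.0% | 31.4% | 5.0-5.6% |
| 83% to 40% | 7.4% | 17.1% | 32.0% | 4.5-5.9% |

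At a fall of 1.5 SD, simulation gives about 13% for 60% to 38% and about 34% for 70% to 30%.

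**Post-CHMI serum.** Here infection itself moves the titre and no waning is involved (n = 39, 49% protected, SD 0.4 log10). Shifts of 0.1, 0.2 and 0.3 log10 give an association at p < 0.05 in 11%, 32% and 60% of trials. A shift of -0.2 gives 31%, so the direction of the effect does not matter.

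**The case against.** **The plan does not state pooling.** True: it is silent. The covariate sentence in section 9.4.5 gives age only as an example and could carry cohort, and section 9.4.1 leaves detail to a SAP not yet written. A reader might infer that a pooled test is prescribed; the text does not go that far. But the named tests have no cohort term and cohort is never mentioned, so the unstratified test is the plain reading.

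**Waning titre alone creates a false correlate.** This is tempting but wrong: protection must differ too. The quoted heterologous results for this regimen (section 1.1) are 5/6 at 3 weeks and 5/6 at 9-10 weeks, which show no fall. They do not exclude one. The exact 95% interval for 5/6 runs from 36% (solving 6p⁵(1 - p) + p⁶ = 0.025) to 99.6% (0.975^(1/6)). The later group had also had an earlier homologous CHMI, and 9-10 weeks is not 12. For a different, five-dose regimen the background quotes 4/5 at 3 weeks (section 2.1.5.1) and 8% at 24 weeks (Table 5, note b). The documents leave the question open, and the trial itself estimates VE at each time point.

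**Bridging is endangered.** A reader might infer this. Sections 1.1 and 2.1.5.1 bridge VE between trials; they do not bridge an antibody correlate.

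**The post-CHMI serum is listed only for measurement.** The synopsis objective does speak of responses following vaccination, and the sample has ordinary immunogenicity value. But section 3.2 puts it in the same sentence as the correlate question and excludes nothing.

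**Stratifying discards signal, and no decision rule is attached.** If antibody mediates protection, part of the between-cohort difference is real, and a stratified test gives that part up. Nor does section 9.4.5 attach a p-value threshold to this analysis. Both points stand and limit the weight of the concern.

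**Conclusion.** The concern holds as an under-specified analysis with two identifiable biases. The unstratified day-of-CHMI test is exposed only if titre and protection both fall between cohorts. It then gives about 6-13% false positives for a 13-22 point fall in protection and up to about 35% for a 40 point fall, against about 5% when stratified. The lower ends go with small titre falls, and the top of the range needs a titre fall of about 1.5 SD. The titre SD, titre falls and cohort protection rates are assumptions, since the documents give none of them, so these figures are illustrative. D15 and D43 are at matched intervals and are not confounded by time since vaccination.

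The post-CHMI serum is a separate matter of reverse causation; its size depends on an unknown effect of infection on titre. Because no primary correlate sample is named, several samples could also each be tested. This should be corrected, but it concerns a secondary objective and leaves the primary VE result as it is.

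**What to change.** In sections 9.4.5 and 9.4.6, and in the SAP before database lock:

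1. Compare protected with non-protected vaccinees by a Wilcoxon test stratified by CHMI cohort (van Elteren), or by a regression for protection with cohort as a factor. Apply the same to any threshold search under section 9.2.
2. Limit candidate antibody correlates to pre-challenge sera (D15, D43, day of CHMI), and name one as primary. D43 is a natural choice because it is V3+14 in both cohorts.
3. Report post-challenge samples descriptively: the CHMI+28 serum (D78/D141) and the CHMI+7 PBMC (D57/D120). Reword the section 3.2 objective so that the post-CHMI serum is measured but is not part of the correlate question.

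The cost is wording, plus a small loss of any true between-cohort signal. No new data or visits are needed.

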9.4.6 ANALYSIS OF CELLULAR RESPONSES, CORRELATES OF PROTECTION

The frequency of T-cells specific to Pf sporozoite and selected pre-erythrocytic antigens will be identified as CD4/CD8 + T-cells expressing cytokines (e.g., IL-2, TNF- α and IFN- γ) upon short term in vitro stimulation with PfSPZ or specific pre-erythrocytic antigens. Results will be expressed as antigen-specific CD4/CD8 T-cells per million respectively of CD4 or CD8+ T-cells. Descriptive statistics (e.g., N, minimum, Q1, median, Q3, maximum, mean, standard deviation) will be tabulated by group, for pre and post vaccination time-points. These results may be presented graphically by box plots.

Correlations with protection will be done using non-parametric tests based on rank, such as the Spearman rank correlation coefficient. Log10 transformed data will be used when a logarithmic transformation results in a distribution more nearly normal than the distribution of untransformed values. Association between categorical measures will be assessed using chi-square or exact tests. Effects of covariates (e.g. age and ethnicity) will be assessed using regression models.

9.4.7 PLANNED INTERIM ANALYSIS

No formal interim analyses are planned.

9.4.8 TABULATION OF INDIVIDUAL PARTICIPANT DATA

Individual safety, immunogenicity, and parasitology data will be listed for each study participant.

10. SUPPORTING DOCUMENTATION AND OPERATIONAL CONSIDERATIONS

10.1 REGULATORY, ETHICAL AND STUDY OVERSIGHT CONSIDERATIONS

This study will be performed under the regulatory oversight of the US FDA. It will be performed under an active IND held by the IND Sponsor, Sanaria Inc. Original protocol approval will be performed by the WCG IRB. This will later be supplemented by oversight provided by NIH Ethics Committee (to oversee the work done at the NIH Clinical Center), the Clinical Ethics Committee at the University of Maryland Medical Center (to oversee the work done at the University of Maryland) or the appropriate IRB for another center if the trial cannot be done as planned at NIH and UMB. Details will depend in part on whether or not there are reliance agreements between WCG IRB and the institutional IRBs.

10.1.1 RECRUITMENT OF PARTICIPANTS

Healthy adult men and women will be recruited from the clinical center area by use of advertisements in multiple media formats, to include, but not limited to: informational flyers, newspaper advertisements, websites, word of mouth, and e-mail. All recruitment materials will be prepared and submitted for review and approval by the IRB prior to use. When a participant calls the study site and discloses an interest in the study, the recruitment staff will discuss the trial from an IRB-approved script. If the participant is still interested, contact information will be obtained and an appointment for briefing and/or screening will be arranged.

10.1.2 INFORMED CONSENT PROCESS

10.1.2.1 CONSENT/ASSENT AND OTHER INFORMATIONAL DOCUMENTS PROVIDED TO PARTICIPANTS

The site-specific informed consent document will be reviewed and approved by the appropriate IRB(s) and regulatory bodies (FDA) prior to initiation of the study. The consent document shall, at a minimum, meet the requirement of 32 CFR 219.116(a)(6) (General Requirements for Informed Consent). The consent document will contain a full explanation of the possible risks, advantages, and alternate treatment options, and availability of treatment in the case of injury, in accordance with 21 CFR 50. The consent document indicates that by signature, the participant permits access to relevant medical records by the Sponsor and by representatives of the IRBs and FDA. The Sponsor will submit a copy of the initial IRB-approved consent form to the FDA and will maintain copies of revised consent documents that have been reviewed and approved by the IRBs.

Informed consent includes the principle that it is critical the participant be informed about the principal potential risks and benefits. This information will allow the participant to make a personal risk versus benefit decision and understand the following:

- Participation is entirely voluntary.
- Participants may withdraw from participation at any time.
- Refusal to participate involves no penalty.
- The individual is free to ask any questions that will allow him/her to understand the nature of the protocol.
- A description of this clinical trial will be available on <http://www.ClinicalTrials.gov>, as required by US law.

10.1.2.2 CONSENT PROCEDURES AND DOCUMENTATION

Informed consent will be obtained from each participant prior to any procedures being performed. The study briefing and informed consent process will be done at the clinical center, which may begin in a group setting, but then proceeds to individual discussion between an investigator and study participant prior to any procedures. Study individuals who are interested in learning about the trial will meet with a member of the study team and will undergo an informed consent process consisting of a detailed informational presentation of the study given by a study investigator or by using IRB approved briefing slides in person or by means of a pre-recorded audio recording. Following the briefing, the coordinator or designee will provide the participant ample time to read the informed consent document. A study investigator and/or designee will answer all questions raised during the session. Any question that cannot be answered will

be referred to the site PI. The participant should understand that the study product is an investigational product and is not licensed by the FDA for commercial use, but is permitted to be used in this clinical research. The participant will be asked to sign the consent. The participant will be allowed to take the consent document home to consider and discuss it with others and return to the clinical center at a later time to sign it. After signing the consent, the participant will take an Assessment of Understanding. The assessment is administered to aid the study personnel in identifying gaps in understanding. Participants must score at least 80% correct on the 20-question multiple-choice questionnaire. Any questions missed will be explained to the participant, and the participant's questions will be answered. The participant will be given one additional opportunity to take the comprehension test. Any participant who, in the opinion of the study investigator, does not understand the study well enough to consider their consent truly informed will be excluded. As the Test of Understanding is in English for the two US sites, passing the test will be considered an adequate assessment of English language comprehension.

Should the protocol be modified, the participant consent document must be revised to reflect the changes to the protocol. If a previously enrolled participant is directly affected by the change, the participant will receive a copy of the revised informed consent document. The approved revision will be read, signed, and dated by the participant.

10.1.3 COMPENSATION FOR PARTICIPATION

Compensation will occur at the time of each designated visit. Compensation will be provided only for completed study procedures designated for compensatory payment. The likely compensation for study participants is shown in **Table 14**

For the post-CHMI malaria phase monitoring follow-up, each participant who is compliant with all of the required daily visits, including all follow-up visits after initiation of treatment for malaria, will receive \$100 per day while they remain PCR negative or during Directly Observed Therapy (x 3 days). Each participant will receive a minimum of \$300 and a maximum of \$1200 depending upon when or if they develop malaria during the post-CHMI period. Participants who remain negative for malaria after the initial post-CHMI malaria monitoring phase will return to the CVD on Days 20, 22, 25, and 28 post CHMI to collect blood for qPCR. Participants who developed and were treated for malaria will return in follow-up on Day 28. Completion of post-CHMI follow-up visits will occur 28 days post-CHMI.

Participants who serve as alternates but who do not undergo immunization will be compensated for the screening visit, visit prior to first immunization and the day when they serve as an alternate \$100.

Compensation \$100 will also be provided for necessary unscheduled and/or supplemental visits.

Table 14. Compensation Plan

Activities	No. of Visits	UMB CVD	
		Compensation per Visit (\$)	Total Compensation (\$)
Screening	1	100	100
Pre-Immunization	1	100	100
Immunization	3	200	600
Memory Aid	4	70	280
Telephone Visit	1	15	15
Post-Immunization Follow-Up ^a	4	100	400
CHMI	1	400	400
Post-CHMI Initial Malaria Monitoring Phase ^b	3-12	[contact]
Additional CHMI Monitoring ^c	1-3	100	100-300
Post-CHMI Follow-Up	2	100	200
Bonus for Completion	1	200	250
Total ^d	28		2,645-3,845

a Number of visits for post-immunization follow-up (prior to CHMI) will vary depending upon the participant's cohort. Cohort A and B may have 7 follow-up visits; Cohort C may have 6 follow-up visits.

b Post CHMI Initial Monitoring Phase will start on Day 7 post-CHMI until Day 18 post-CHMI.

c qPCR will be collected on Days 20, 22, 25 and 28 post CHMI for participants who remain malaria negative. Those participants who develop malaria will return for directly observed therapy for three days and will return on D28.

d Total compensation is approximate as the total number and type of visits will be unique for each participant.

Amounts of compensation may exceed the planned maximum amounts if compensated unplanned visits are required (e. g., to evaluate AEs).

